The study is a single blind randomized cross-over design. Subjects (up to 68 healthy men and women) will participate in the study (48 non-smokers and 10 smokers in the main study and 5-10 in the pilot study). Eligible subjects will have 5 clinic visits: one screening visit, 2 exposure visits, and 2 post-exposure sample collection visits. Each subject will participate in 2 exposure sessions, one to clean air (ozone<5ppb) and one to 0.2 ppm ozone in the Controlled Exposure Facility (CEF) at the Environmental and Occupational Health Sciences Institute (EOHSI). The order of the exposure sessions will be randomized. Up to 2 subjects may participate in each exposure session. Induced sputum samples will be collected at the baseline (during screening) then at one of three pre-selected time periods (24, 48 or 72 hours) following each exposure session. Breath, blood, oral washes, oropharyngeal swabs, and urine samples will be collected at each visit.

Subjects will undergo telephone screening. If eligible they will be scheduled for the screening visit. Subjects will be asked to refrain from antioxidants, over the counter anti-inflammatory medications, strenuous exercise, alcohol, home air purifiers, unvented household combustion sources, gases and fumes for 48 h prior to the screening visit and before each exposure visit through the post-sample collection period. Non-smokers will also be asked to avoid tobacco smoke.

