At screening, subjects will be asked to provide an induced sputum specimen (baseline sample), which will be immediately analyzed for the presence of plugs. Using the method described by Pin et al. [36] and Alexis et al., [37] subjects inhale increasing concentrations of saline (3%, 4% and 5%) for 3 consecutive 7-minute periods through a mouthpiece without a valve. To reduce the risk of bronchospasm, following the recommendations of the European Respiratory Commission [38], albuterol (180 mcg; 2 puffs of a standard metered inhaler) will be given to subjects 15 minutes prior to the start of the induction. Post-dose spirometry is performed to obtain a baseline FEV-1. The subject will be asked to breathe through his/her mouth during the induction. If the subject is observed to breathe through his/her nose, he/she will be asked to monitor his/her breathing and will be offered a nose clip to use during the induction. After each period of inhalation, an FEV-1 is measured for safety. If the FEV-1 decreases by 20% or more from the post-dose FEV-1, the procedure is stopped. After rinsing the mouth, swallowing water and blowing the nose to minimize contamination by saliva or post nasal drip, subjects will cough sputum into a sterile container. Subjects unable to provide an adequate specimen (70-75 mg of plugs) will be excused from the study. In the main study, subjects will be assigned to a post-exposure sample collection time (24, 48, or 72 hours) to be used for both exposure sessions. In the pilot study and for all smokers, all subjects will be assigned to the 24 hour post-exposure sample collection. The exposure sessions will be scheduled.

Subjects may be screened (telephone and screening visits) year-round. For the main study, the exposure visits will be scheduled between October and June, consistent with low ambient ozone months in New Jersey. For the pilot study, since only acute responses are examined (24 hours of the exposure), the screening and exposure visits will take place year-round. If over six months have passed between the screening visit and scheduling the exposures, those subjects will be re-consented and the screening visit will be repeated.

Each exposure session will be 3 hours in duration. Subjects will be called the day prior to the visit to confirm the appointment. If unable to be reached by phone, reminder texts or emails may be sent from a Rutgers-authenticated computer. Subjects will be asked to report any

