current or recent respiratory symptoms. If subjects report any symptoms within the previous 4 weeks, the visit will be rescheduled. Subjects will be asked to refrain from eating for 2 hours prior to the exposure visit. At the start of the visit, the subject's blood pressure, pulse, and temperature will be measured. IOS and spirometry will be performed before and after the exposure session. Two questionnaires will also be administered before the exposure session: a stress questionnaire and a symptom questionnaire. If the subject reports the presence of any respiratory symptoms, the exposure session will be canceled. During the exposure, heart rate will be measured using a wireless monitor (H7; Polar USA). Subjects will be asked to alternate (every 15 minutes) rest and mild/moderate exercise periods on a cycle ergometer to maintain an average heart rate of approximately 60% maximum heart rate (220-age). The exercise is necessary as healthy human subjects are relatively insensitive to ozone [39, 40]. The exercise schedule may be modified to maintain the ventilation rate or for the subject's comfort. After the exposure session, the stress and symptom questionnaires will be administered. An exposure type questionnaire will also be administered immediately after the exposure. If the subject reports any physical symptoms or has a 20% decrease in his/her FEV1 after the exposure session, the study physician will be consulted. Subjects will be given verbal and written instructions to contact the Robert Wood Johnson Medical School Pulmonary Division if they experience any breathing problems after leaving EOHSI. Subjects will inform the responding pulmonologist that he/she is a study subject. As an additional precaution, subjects will be given a rescue inhaler to use only if directed to do so by the responding pulmonologist. Subjects will be shown how to use the inhaler prior to leaving the EOHSI clinic. The pulmonologist will inform [name] of any calls made to the pulmonologist and any treatment. The symptom questionnaire will be administered to each subject the day after exposure. For subjects returning at 24 hours for the post-exposure sputum sample, the questionnaire will be administered in person. For all other subjects the questionnaire will be administered by phone. As a secondary check, the questionnaire will ask the study subject if he/she contacted the Pulmonary Division. If the subject reports the presence of any symptoms or called the Pulmonary Division, the study physician will be consulted, prior to the collection of any samples.

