
Immediately before and after each exposure session EBC samples will be collected using the same methods as in the screening visits. In addition to the EBC samples, urine, oral washes, oropharyngeal swabs, and blood samples will be collected before and after each exposure session. During the second exposure visits, an additional blood sample will be collected for genotyping of GST polymorphisms. The urine samples will be analyzed for eicosanoids and other markers of inflammation. The blood samples will be processed by either [name] lab (research blood for future use) or the Rutgers University Cell and DNA Repository facility core at EOHSI (sample for genetic analysis).

Subjects will be asked to return for a follow-up visit either 1, 2, or 3 days after each exposure visit. Subjects will be asked to refrain from eating for 2 hours prior to the visit. The blood pressure, pulse rate, and oral temperature will be checked. IOS and spirometry will be performed and an induced sputum sample will be collected. The symptom and stress questionnaire will be administered. The blood, urine, oral washes, oropharyngeal swabs, and EBC samples will also be collected.

Sputum samples obtained after the ozone exposure may be compared with samples collected either at the screening visit or after the clean air exposure. If the subject is randomized to ozone exposure first and is unable to produce a sputum sample after the ozone exposure, the subject will be withdrawn from the study.

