De-identified data will be entered into Excel worksheets. The data will be stored on the EOHSI secure shared drive. All data will be double-entered by two different investigators. All discrepancies in the data will be resolved by a third investigator. Only de-identified data will be transmitted between study investigators..

7. *Statistical Analysis*

Descriptive statistics, including means, standard deviations, and histograms will summarize the distributions of markers stratified by time point and exposure. Analysis of covariance (ANCOVA) will be used to compare the means of markers of inflammation. Specifically, with baseline level as a covariate in the model, F-tests will test whether the means are significantly different following exposure to ozone or clean air at each follow-up time-point. The mean fold-changes (or log-fold-changes if necessary to meet normality assumptions) in M1 and M2 macrophages will also be assessed at each time-point (24, 48 or 72 h) following ozone and compared to clean air in humans.

8. *Data and Safety Monitoring*

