Statistical Analysis Plan

Activated Macrophages and Ozone Toxicity

NCT02673775

June 7, 2023

Primary Outcome Measure: Concentrations of M1 and M2 macrophages in the sputum 24 hours after exposure.

Measure Description: The relative concentrations of M1 and M2 macrophages in the induced sputum sample will be assessed.

Statistical method: A paired t-test, with ratio of M2 to M1 macrophages in the induced sputum sample as the dependent variable, was used to compare the effect of ozone and clean air 24 hours after exposure. The level of significance (α) was set to 0.05.

Primary Outcome Measure: Concentrations of M1 and M2 macrophages in the sputum 48 hours after exposure.

Measure Description: The relative concentrations of M1 and M2 macrophages in the induced sputum sample will be assessed.

Statistical method: A paired t-test, with ratio of M2 to M1 macrophages in the induced sputum sample as the dependent variable, was used to compare the effect of ozone and clean air 48 hours after exposure. The level of significance (α) was set to 0.05.

Primary Outcome Measure: Concentrations of M1 and M2 macrophages in the sputum 72 hours after exposure.

Measure Description: The relative concentrations of M1 and M2 macrophages in the induced sputum sample will be assessed.

Statistical method: A paired t-test, with ratio of M2 to M1 macrophages in the induced sputum sample as the dependent variable, was used to compare the effect of ozone and clean air 72 hours after exposure. The level of significance (α) was set to 0.05.

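### The ANCOVA in Protocol section 7 names no subject term in a cross-over, so its error bars are too wide; the sputum control and the period effect also need settling

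*Protocol*

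**What the plan says.** **Design.** Protocol section 3 describes a single-blind cross-over with one ozone and one clean-air session per subject: "The order of the exposure sessions will be randomized". Each main-study subject has one collection time (24, 48 or 72 h) for both sessions. Each therefore gives two post-exposure sputum samples and one baseline sputum sample, taken at screening.

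**Protocol section 7.** For markers of inflammation: "with baseline level as a covariate in the model, F-tests will test whether the means are significantly different" after ozone or clean air at each follow-up time. Fold-changes in M1 and M2 are assessed "following ozone and compared to clean air in humans". No subject, repeated-measures or period term is named.

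**SAP.** For the M2:M1 ratio, a paired t-test "was used to compare the effect of ozone and clean air 24 hours after exposure", with the same wording at 48 and 72 h. Pairing deals with subject. No period term is named.

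**Control for sputum, Protocol section 3.** "Sputum samples obtained after the ozone exposure may be compared with samples collected either at the screening visit or after the clean air exposure". No rule for choosing is given.

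**Timing of screening, Protocol section 3.** "Subjects may be screened (telephone and screening visits) year-round. For the main study, the exposure visits will be scheduled between October and June". The screening visit is repeated "If over six months have passed between the screening visit and scheduling the exposures". Exposure sessions include "mild/moderate exercise periods on a cycle ergometer"; screening does not.

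**The concern.** Section 7 compares ozone with clean air on two values from the same person, but the only adjustment it names is baseline. If the two records are treated as independent, the residual keeps between-subject variation that a cross-over is designed to remove. The sputum baseline does not absorb all of it. The error bars on every section 7 marker comparison would then be misstated.

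The open control is a different matter. Only the order of the two sessions is randomised, so a contrast against screening is not a randomised comparison. It mixes ozone with visit order, season, chamber and exercise.

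The period term is the usual third element of a two-period analysis. Without it, any drift between sessions goes into the error. If complete pairs are unequal between sequences, it also goes into the estimate.

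**Working it through.** **1. The plan's own figure.** Section 3.3 gives 16 per exposure group for 90% power with 0.05-level two-group t-tests. The SD of change is √(2(1-ρ)SD²), which equals SD at ρ = 0.5. The figure can be neither reproduced nor refuted, because the sample size behind the quoted SE of 8% is not given and so the SD is unknown. The point does not depend on it. Working back, a two-group t-test with 16 per group and 90% power needs a standardised effect of 1.18.

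**2. Standard error of the section 7 ANCOVA, shared baseline (sputum).** Assume that the three values (screening, ozone, clean air) have equal SD and common correlation ρ. Both analyses estimate the same mean difference.
- Paired: SE² = 2·SD²(1-ρ)/n.
- ANCOVA with baseline only: residual variance is SD²(1-ρ²), so SE² = 2·SD²(1-ρ²)/n.
- Ratio of SEs = √[(1-ρ²)/(1-ρ)] = √(1+ρ).

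Simulated results at n = 16:

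| ρ | √(1+ρ) | Type I error |
|---|---|---|
| 0.3 | 1.14 (simulated 1.13) | 3.0% |
| 0.5 | 1.22 (simulated 1.21-1.22) | 2.0% |
| 0.7 | 1.30 | 1.3% |

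Breath condensate, urine and blood are also sampled before each session. If that session's own baseline is used, the excess in SE is smaller: 3-10%, with type I error 3.2-4.5%, over the correlation patterns tried.

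**3. Power cost.** The documents give neither the effect on these markers nor the SD. As an illustration, take ln(1.6/2.3) = -0.36, which reads the section 3.3 fold-changes for CD16 and CD14 as an effect on the log M2:M1 ratio. Two SDs of the within-subject difference are used:
- 0.36/1.18 ≈ 0.31, the value implied if the two-group calculation in section 3.3 is taken at face value.
- 0.43, at which 16 pairs give 88% power.

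| SD of difference | Paired | ANCOVA, ρ = 0.3 / 0.5 / 0.7 |
|---|---|---|
| 0.31 | 99.3% | 98.9 / 98.3 / 97.5% |
| 0.43 | 88.4% | 84.7 / 80.6 / 76.0% |

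The loss is under 2 points in the first row and about 4-12 points in the second.

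**4. The two controls side by side.**

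| | Clean-air sample | Screening sample |
|---|---|---|
| Order relative to ozone | randomised | always first |
| Season (main study) | October-June | any month |
| Chamber and cycling beforehand | yes | no |
| Time from exposure | assigned 24, 48 or 72 h | none; up to six months before scheduling without repeat |
| 48 h restrictions | yes | yes |

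Every contrast with a named test uses clean air. What remains open is sputum outcomes listed in section 4.2 with no named test, for example phagocytosis, oxidative burst and microbiome aliquots.

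**5. Period.** Let s be the shift from session 1 to session 2. The paired mean difference is biased by s × (clean-air-first pairs - ozone-first pairs)/total. At 8:8 the bias is 0; at 11:5 it is 6/16 = 0.375 of s. The table assumes n = 16, SD 0.43 and no ozone effect. The period-adjusted test stays at about 5% throughout.

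| Split | Shift | Type I error, paired t | Bias |
|---|---|---|---|
| 8:8 | 0.18 | 3.4% | 0 |
| 8:8 | 0.36 | 1.2% | 0 |
| 10:6 | 0.18 | 5.0% | 0.045 |
| 11:5 | 0 | 5.0% | 0 |
| 11:5 | 0.09 | 5.5% | 0.03 |
| 11:5 | 0.18 | 6.8% | 0.07 |
| 11:5 | 0.36 | 9.6% | 0.14 |

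At 11:5 and shift 0.18, type I error is 8.3% if the SD is 0.30 and 6.1% if it is 0.60. At 8:8 with an effect of -0.36, paired against adjusted power is 84% against 88% at shift 0.18, and 71% against 88% at shift 0.36. If simple randomisation were used (an assumption; no method is stated), a split of 11:5 or worse among 16 has probability 21%. Averaged over all splits, type I error is 5.0%.

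**The case against.** The strongest reply is that section 7 is a one-paragraph summary that never says the two records are independent. The SAP pairs by subject for all three primary outcomes, and the error is on the safe side in any case. Much of this stands. The text is silent rather than explicitly wrong, and no false claim follows from a conservative test. But the SAP covers only the M2:M1 ratio, so it does not supply the missing structure for the section 7 markers.

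On the control, section 3 is permissive and names no test, and section 7 already uses baseline as a covariate. A reader might infer that the trial could declare an ozone effect against screening. Large false-positive rates can be calculated for such a test (35% for a non-ozone shift of 0.18 at SD 0.43, n = 16), but no section plans one. The gap is confined to outcomes with no named test.

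On period, a reader might infer that the paired t-test is invalid, or that uneven sequences alone bias it. Neither holds. With no shift, an 11:5 split gives 5.0% and no bias, and 10:6 does not exceed 5.0% even at shift 0.18. The documents state neither a shift nor an imbalance. Nor does the section 3 withdrawal of ozone-first subjects without post-ozone sputum unbalance the sputum pairs, since those subjects have no complete pair to lose. It can remove ozone-first pairs for breath condensate, urine and blood. The stop in section 4.4 after bronchospasm on clean air works the other way, but that section calls the event unlikely. A pre-specified paired t-test in a randomised cross-over is a legitimate choice.

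**Conclusion.** The main point holds for Protocol section 7. Fitted as written to sputum markers, the ANCOVA overstates the standard error by about 13-30% (about 21-22% at the correlation of 0.5 in section 3.3) and runs at about 1.3-3% type I error. This assumes equal SDs and one common correlation. The loss of power cannot be fixed from the documents: under 2 points at a difference SD of about 0.31, and 4-12 points at 0.43, for n = 16 and an assumed effect of 0.36.

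The control wording in section 3 conflicts with section 7 and the SAP and must be reconciled, but it affects only sputum outcomes with no named test. The missing period term is minor. It costs power when sequences balance and there is a shift. It takes type I error above 5% only when a marked imbalance (about 11:5 or worse of 16) and a material shift occur together.

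A reader might go further and conclude that the primary result is unsound or that section 7 inflates false positives. The documents support neither: the SAP tests use clean air and pair by subject, and the missing subject term makes section 7 conservative.

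**What to change.** 1. **Section 7.** Replace the ANCOVA with a within-subject model: exposure and period fixed, subject random, and baseline as a covariate where useful. State which baseline applies to each sample type.
2. **Section 3.** Reconcile with section 7 and the SAP by stating that the clean-air sample at the same time point is the control for inferential contrasts, and that screening values serve as covariate or description.
3. **SAP.** Keep the paired t-test and report beside it a sensitivity analysis labelled as period-adjusted. This suits a plan already written in the past tense. Report complete pairs by sequence, separately for sputum and for the other samples.

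The cost is one protocol sentence, revised wording in section 7, and one added analysis. The period term uses one degree of freedom. With no shift it costs about 0.4 points of power at 8:8 and 5-6 points at 11:5 (n = 16, SD 0.43). No withdrawal or stopping rule needs to change for this.

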3.1. Duration of Study

The study duration is expected to be four years. Each person will have 5 visits (one screening visit, two exposure visits, and two post-exposure visits) to the EOHSI clinic, for a total time of approximately 15 hours.

3.2 Study Sites

The consent, screening, exposure sessions and sputum collection will take place at EOHSI. All consent forms and identifiable data will also be stored at EOHSI. Analysis of de-identified data will take place at the Ernest Mario School of Pharmacy and at the School of Public Health.

3.3 Sample Size Justification

Calculations are based on published human exposure studies [41, 42] demonstrating 2.3-fold and 1.6-fold increases (SE=8%) in mean fluorescence intensity of sputum leukocyte expression of markers of M1 (CD14) and M2 (CD16) macrophages following ozone exposure at 24 h compared to clean air. The SDs for changes [the square root of $2(1-\rho)\text{SD}^2$] were calculated where rho is the intra-person correlation (0.5) between measurements. Based on this, 16 subjects/exposure group are needed to achieve 90% power using 0.05 level two-group t-tests.

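### The 90% power in protocol section 3.3 is for single-marker intensity at 24 h and cannot be attached to any of the SAP's three primary tests on the M2/M1 ratio; the planned sample size is also given in two versions

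*Protocol*

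**What the plan says.** Protocol section 3.3 rests on published human exposure studies of "markers of M1 (CD14) and M2 (CD16) macrophages following ozone exposure at 24 h compared to clean air". It cites 2.3-fold and 1.6-fold rises with an SE of 8%, takes a within-person correlation of 0.5, and concludes: "Based on this, 16 subjects/exposure group are needed to achieve 90% power using 0.05 level two-group t-tests".

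The SAP lists three primary outcomes, one per sampling time. The method for each is "A paired t-test, with ratio of M2 to M1 macrophages in the induced sputum sample as the dependent variable", and the last of the three "was used to compare the effect of ozone and clean air 72 hours after exposure". For each, "The level of significance (α) was set to 0.05".

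Protocol section 7 differs again. "Analysis of covariance (ANCOVA) will be used to compare the means of markers of inflammation", with baseline as covariate. For the macrophages it says that "The mean fold-changes (or log-fold-changes if necessary to meet normality assumptions) in M1 and M2 macrophages" will be assessed at each time and compared with clean air. It names no test for that comparison and does not mention the ratio.

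Under section 3, main-study "subjects will be assigned to a post-exposure sample collection time (24, 48, or 72 hours) to be used for both exposure sessions", so each subject contributes a pair at one time only. All smokers are assigned to 24 h. Section 3 gives 48 non-smokers and 10 smokers in the main study, 5 to 10 pilot subjects, and up to 68 in all. Section 3.4 gives 60 main-study non-smokers, 10 smokers, up to 10 pilot subjects, and up to 80 in all.

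**The concern.** A power figure is a property of a particular test on a particular endpoint with a stated effect and SD. The endpoint in section 3.3 differs from the SAP's at all three times, and its time point differs at two. The test is also labelled differently, although that is the least important mismatch.

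What is at stake is how a non-significant result would be read. The 90% is the only justification of size in either document. A reader who meets a null on the ratio could take it as coming from a test with 90% power, and the documents contain no inputs for that reading at any time. The two planned sizes add to this, because the number of pairs behind each test cannot be fixed from the text.

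**Working it through.** **1. The plan's own figure.** With correlation 0.5, the SD of a change is √(2 × (1 − 0.5)) × SD = SD. By the noncentral t distribution (two-sided 0.05, assumed because sidedness is not stated), 16 per group with 90% power in a two-group t-test corresponds to a standardised effect of 1.185.

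Whether the stated inputs lead to 16 cannot be settled, because the size m of the source studies and the scale of the 8% SE are not given. Taking SD = 0.08 × √m:

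- CD16 on the log scale: effect ln 1.6 = 0.470. With m = 24, SD = 0.392 and n = 16 per group; m = 10 gives 8, and m = 40 gives 26.
- CD16 on the raw scale: effect 0.6. With m = 40, SD = 0.506 and n = 16 per group.

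So 16 is neither confirmed nor refuted, and no arithmetic error is claimed.

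**2. Is the two-group label the problem?** No. Applying the same standardised effect of 1.185 to 16 paired differences gives power of 99.3%. For a single marker the label is conservative.

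**3. What is available for the primary tests.**

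| | Section 3.3 | SAP primary tests |
|---|---|---|
| Endpoint | CD14 intensity, CD16 intensity | M2/M1 ratio |
| Time | 24 h | 24, 48, 72 h |
| Test | two-group t | paired t |
| Effect and SD basis | fold rises, SE 8%, correlation 0.5 | none given |

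Power cannot be computed for the right-hand column. What can be computed is the detectable effect.

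**4. Pairs per time point.** Assuming an equal split over the three times and no loss, 48/3 = 16 and 60/3 = 20. If the 10 smokers enter the 24 h test, these become 16 + 10 = 26 and 20 + 10 = 30. If 48 and 60 are enrolled numbers, all of these are ceilings. Section 3 withdraws a subject who has ozone first and then produces no sputum. Section 4.4 stops a subject who has bronchospasm with clean air before the ozone session.

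**5. Detectable effect and precision.** The detectable value is the mean paired difference divided by its SD that gives 90% power (noncentral t, n − 1 df, two-sided 0.05, no multiplicity adjustment). The 95% CI half-width, in units of the same SD, is t(0.975, n − 1)/√n.

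| Pairs | Detectable at 90% | t(0.975, n − 1) | CI half-width |
|---|---|---|---|
| 16 | 0.87 | 2.131 | 2.131/4 = 0.53 |
| 20 | 0.76 | 2.093 | 2.093/4.472 = 0.47 |
| 26 | 0.66 | 2.060 | 2.060/5.099 = 0.40 |
| 30 | 0.61 | 2.045 | 2.045/5.477 = 0.37 |

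At 16 pairs the requirement would be 0.77 for a one-sided test, or 1.02 if 0.05 were divided by three.

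**6. How wide the uncertainty is.** With 16 pairs, power is 46% at a standardised difference of 0.5, 61% at 0.6, 85% at 0.8, 96% at 1.0 and 99.3% at 1.185. The documents do not say where in this range the ratio falls.

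**7. The two sizes.** 48 + 10 + 10 = 68 and 60 + 10 + 10 = 80. The whole difference is in the main-study non-smokers. 48/60 = 0.80, so a 20% loss would link the two figures, but no loss allowance is stated.

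**The case against.** Several points on the other side are sound. The SAP already settles which tests are primary; section 7 designates nothing as primary, ties ANCOVA to markers of inflammation, and leaves the M1/M2 comparison without a test. A paired test can be read as filling that gap, so what remains to align is mainly the ratio. Section 3.3 is itself partly a within-person calculation, since it uses an SD of change. Section 2 says the sequential M1/M2 hypothesis had not been tested before, so planning from published 24 h marker data was a reasonable proxy. Neither document expressly claims 90% for the ratio tests. Section 3 speaks of participating and section 3.4 of recruiting, and subjects without adequate sputum are excused at screening, so recruited versus participating is a plausible account of 48 and 60. The SAP is dated June 2023 and written in the past tense, so rewording section 3.3 alters no data.

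These points narrow the matter but leave its core. A proxy may be reasonable, but the extrapolation to another endpoint and two later times is not stated, and neither is the reason for the two sizes.

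A reader might infer more than the text allows:

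- **That the primary tests are underpowered.** The effect and SD of the ratio are unknown, so power could be above or below 90%.
- **That power is lost because both markers rise and partly cancel (1.6/2.3 = 0.70).** Intensity is not a cell ratio, and power depends on an SD that is not given; a smaller SD for the ratio could offset a smaller effect.
- **That loss leaves about 13 pairs (16 × 0.8 = 12.8; detectable 0.98).** This is purely an assumed loss, and it counts the same 20% twice if 48 is already 60 after loss.
- **That enrolment is adequate.** The same missing inputs prevent that conclusion too.

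**Conclusion.** The point holds as a mismatch between documents, and it should be fixed. The only stated power applies to single-marker intensity at 24 h; it cannot be carried to any of the three primary ratio tests. The substantive gap is the endpoint and the two later times, not the two-group label. On the SAP's tests, 90% power requires a standardised within-person difference of 0.87 with 16 complete pairs or 0.76 with 20, and 0.66 or 0.61 at 24 h if the smokers are included. These figures assume a two-sided 0.05 test without multiplicity adjustment, an equal split over the three times, and no loss of pairs.

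Separately, 48/68 and 60/80 contradict each other as written. Labelling them as participating and recruited would probably resolve this, but the protocol does not do so.

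**What to change.** 1. In section 3.3, state that the 90% applies to single-marker CD14 and CD16 intensity at 24 h only, and that no effect was assumed for the M2/M1 ratio or for 48 h and 72 h.
2. For the SAP tests, give the standardised within-person difference detectable with 90% power: 0.87 with 16 complete pairs, 0.76 with 20. State the assumptions (two-sided 0.05, no multiplicity adjustment) and update the figure to the actual complete pairs at each time.
3. Report each ratio comparison with its number of pairs and a 95% CI, so that a null is read from the interval and not from a power figure.
4. Align section 7 with the SAP's designated primary analysis: name the ratio and the paired test there, and keep ANCOVA for the markers of inflammation.
5. Reconcile 48/68 with 60/80, labelling recruited versus completing, and state any loss allowance. Say whether the 10 smokers enter the 24 h test.

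The cost is a few sentences in protocol sections 3, 3.3, 3.4 and 7 and in the SAP, plus confidence intervals in the report. The primary test does not change, and no change to enrolment is proposed.
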